- For additional 72 hours after AMG 596 step dose if necessary

Cycle 2 and all subsequent cycles:

- For at least the first 72 hours of AMG 596 infusion in both Arm 1 and Arm 2
- For additional 72 hours after AMG 596 step dose if necessary.

Hospitalization may be shortened to 48 hours from the 6th cycle onwards at the discretion of the investigator.

AMG 404 can be administered in an outpatient setting starting from cycle 1 [REDACTED] onwards. Subjects should be monitored intensely in hospital or outpatient clinic for at least 4 hours after start of each AMG 404 infusion from cycle 1 [REDACTED] onwards.

Restart of infusion should be performed in the clinic/hospital under the supervision of the investigator or designee and the subject should be hospitalized for a minimum of 24 hours when the infusion interruption meets the following criteria:

- associated to an AE, or
- interruption > 24 hours due to a pump related issue.

Dosing with AMG 596 or the combination of AMG 596 and AMG 404 can continue unless the subject becomes intolerant to investigational product, the signs and symptoms of clinical progression are evident as determined by the investigator, or the subject withdraws consent. Tumor evaluations by MRI will occur every 10 to 12 weeks from treatment initiation. Earlier assessments can be made if clinically indicated at the discretion of the investigator. Modified RANO criteria will be used allowing subjects to stay on study until discontinuation criteria are met. Upon discussion with the Sponsor, subjects may continue to receive treatment beyond

radiographic confirmation of progressive disease as long as they continue to derive clinical benefit and until further increase in tumor burden. For analyses purpose, date of progressive disease (PD) is the date of initial observed clinical or radiographic PD.

Assessments during the course of the study include: Clinical evaluation (physical examination, Eastern Cooperative Oncology Group [ECOG] status, height, and weight), vital signs, pulse oximetry, neurological evaluation, electrocardiogram (ECG) triplicate measurement, laboratory assessments (including serum pregnancy test, if applicable, coagulation, hematology, chemistry, urinalysis, hepatitis serology, human immunodeficiency virus (HIV) test, [REDACTED])

[REDACTED] For a full list of study procedures, including the timing of each procedure, please refer to [Section 7](#) and the [Section 7.1](#) Schedule of Assessment.

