7.9 Imaging Assessment of Disease Burden

7.9.1 Magnetic Resonance Imaging (MRI)

MRI of the brain will be done at screening, every 10 to 12 weeks from start of treatment and at SFUP or until the signs and symptoms of clinical progression are evident as determined by the investigator, radiographic progression is confirmed in 2 scans ≥ 4 weeks apart without signs of clinical benefit, start of a new treatment, death or the subject withdraws consent (see [Section 7.1](#) Schedule of Assessment). Upon discussion with the Sponsor, subjects may continue to receive treatment after radiographic confirmation of progressive disease as long as they continue to derive clinical benefit and until further increase in tumor burden. For analysis purposes, date of PD is the date of initial observed PD. All scans for each subject will be performed in the same manner as at baseline, at the same field strength, preferably on the same scanner. The same contrast agent should be used through the study; macrocyclic gadolinium agents are preferred. Scans should be acquired with a slice thickness ≤ 5 mm. At each imaging timepoint, the following sequences will be performed:

- Axial Pre Contrast (2D) T1
- Axial T2
- Axial T2/FLAIR
- Axial Post Contrast (2D) T1

- Axial diffusion-weighted magnetic resonance imaging (DWI) (at selected sites)
- Sagittal Post Contrast (3D) T1 (selected sites if part of site protocol)

Subjects who demonstrate an objective response or disease progression will have a confirmatory MRI performed at least 4 weeks after the initial observation scan.

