8.3.2 Reasons for Removal From Study

Reasons for removal of a subject from the study are:

- decision by sponsor (eg, product quality issue)
- withdrawal of consent from study
- death
- lost to follow-up
- start of any other antitumor therapy

Approved

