| Sequences for this protocol | 
 - Axial Pre Contrast (2D) T1 - Axial T2/FLAIR - Axial T2 - Axial Post Contrast (2D) T1 - Axial DWI (at selected sites) - Sagittal Post Contrast (3D) T1 (at selected sites) |
| Measurement technique | Bidimensional; sum of products of perpendicular diameters |
| Imaging intervals | Screening, every 10-12 weeks, SFUP, LTFU |
| Measurable lesions | Contrast-enhancing lesions with ≥ 10 mm longest diameter and ≥ 10 mm perpendicular diameter |
| Measurable disease | One to five index lesions |

Table 22. Response Assessment

| All % changes are calculated as change from baseline burden, except PD which is baseline or nadir. | |
|--|--|
| Complete response (CR) | 
 • Disappearance of all enhancing disease • no new lesions • stable or improved T2/FLAIR • no more than physiological steroids • clinically stable or improved • Disappearance confirmed with follow-up scan after ≥ 4 weeks |
| Partial response (PR) | 
 • $\geq 50\%$ decrease in the sum of perpendicular diameters of enhancing disease from baseline • stable or improved T2/FLAIR • stable or decreased steroid dose • clinically stable or improved • Decrease confirmed with follow-up scan after ≥ 4 weeks |
| Stable disease (SD) | 
 • Changes do not qualify for CR, PR or PD • stable or improved T2/FLAIR • stable or decreased steroid dose • clinically stable or improved |
| Progressive disease (PD) | 
Any of the below
 
 • $\geq 25\%$ increase in the sum of perpendicular diameters of enhancing disease from the lesser of baseline or nadir • or substantially worsened T2/FLAIR • or unequivocal progression in new lesions • or substantial clinical decline • Increase confirmed with follow-up scan ≥ 4 weeks after initial observation. |

Reponses (CR and PR) are dated at time of confirmation scan.

Progression (PD) is backdated to initial observation, if confirmed.

Approved

Patients with a neurological decline attributable to their underlying tumor requiring discontinuation of treatment without objective evidence of measurable radiographic disease progression at that time should be classified as having “clinical deterioration.” Every effort should be made to document the radiographic progression even after discontinuation of treatment.

Approved

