Subjects who withdraw consent to participate in the study prior to achieving objective response will be censored at their last evaluable radiological assessment date.

End of study:

Primary Completion:

The primary completion of study will occur when the last subject is assessed or receives an intervention for the purposes of final collection of data for the primary analysis. (The primary analysis will occur when target enrollment in Part 1 and Part 2 is complete and each subject either completes 6 months on study or withdraws from the study.)

End of Study:

The time when the last subject is assessed or receives an intervention for evaluation in the study. (The final analysis will occur at this time.)

Enrollment:

A subject is considered enrolled after meeting all eligibility criteria and treatment and cohort have been assigned for the study.

See protocol section 5.0 for further details.

Investigational Product:

The term investigational product is used in reference to AMG 596.

Maximum Tolerated Dose (MTD):

The MTD is defined as the maximum dose with the highest probability of the target toxicity probability interval (TPI), but with a less than 0.25 probability of an excessive or unacceptable TPI.

The target TPI is (0.20, 0.33] and TPIs of (0.33, 0.60] and (0.60, 1.00] are defined as excessive and unacceptable, respectively.

Overall Survival (OS):

The number of days from the date of first administration of AMG 596 to the date of death, regardless of cause.

Subjects who withdraw from treatment without withdrawing consent will be followed for survival status whenever possible. Subjects who are alive (no record of death) and are lost to follow-up will be censored at the date of last contact.

Objective Response (OR):

Tumor response assessment of either complete response or partial response (CR or PR) per modified RANO criteria.

Progression Free Survival (PFS):

The number of days from the date of first administration of AMG 596 to the date of radiological evidence of disease progression (date of MRI scan) or death, regardless of cause.

The following censoring strategies for missing assessment dates will be used for the progression free survival analysis:

If a subject's disease has not progressed and the subject is alive, progression-free survival time will be censored at the last date they are known to be progression-free (ie, the last evaluable radiological assessment date).

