If a subject has no tumor evaluation in the study, progression-free survival time will be censored at the date of the first administration of AMG 596.

Subjects who withdraw consent to participate in the study prior to disease progression will be censored at their last evaluable radiological assessment date.

Response Criteria (per modified RANO):

Complete Response (CR):

- Disappearance of all enhancing disease
- No new lesions
- Stable or improved T2/FLAIR
- No more than physiological steroids
- Clinically stable or improved
- Disappearance confirmed with follow-up scan after ≥ 4 weeks

Partial Response (PR):

- $\geq 50\%$ decrease in the sum of perpendicular diameters of enhancing disease from baseline
- Stable or improved T2/FLAIR
- Stable or decreased steroid dose
- Clinically stable or improved
- Decrease confirmed with follow-up scan after ≥ 4 weeks

Stable Disease (SD):

- Changes do not qualify for CR, PR or PD
- Stable or improved T2/FLAIR
- Stable or decreased steroid dose
- Clinically stable or improved

Progressive Disease (PD):

Any of the below

- $\geq 25\%$ increase in the sum of perpendicular diameters of enhancing disease from the lesser of baseline or nadir
- Or substantially worsened T2/FLAIR
- Or unequivocal progression in new lesions
- Or substantial clinical decline
- Increase confirmed with follow-up scan ≥ 4 weeks after initial observation.

Screening Date:

Screening date is defined as the date the informed consent was signed.

Study Day 1:

Day 1 is defined as the first day that investigational product is administered to the subject. The day before Day 1 is referenced as Day-1.

Study Day:

Post day of dose: study day = (study date - date of Study Day 1) + 1

Pre day of dose: study day = (study date – date of Study Day 1)

Time to Response:

Time to response is calculated as the number of days from the date of first administration of AMG 596 to the date of confirmation of first objective response per MRI scan (date of confirmation of first objective response – date of first dose of AMG 596+1).

If a subject did not respond, time to response will be censored at the date of the last evaluable response assessment.

If a subject has no tumor evaluation related to response assessment as per modified RANO criteria, time to response will be censored at the date of the first administration of AMG 596.

Time to Progression:

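### The documents conflict on whether radiographic PD must be confirmed to count for PFS and TTP, and no rule covers a first PD scan that is never repeated

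*Protocol*

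**What the plan says.** **Where confirmation is required.** Table 22 in protocol Appendix D, the Progressive Disease entry in SAP Section 5 and the table in SAP Appendix D all carry the same line: "Increase confirmed with follow-up scan ≥ 4 weeks after initial observation". Both appendices then date progression conditionally: "Progression (PD) is backdated to initial observation, if confirmed".

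**Where it is not.** The protocol synopsis (Procedures) states: "For analyses purpose, date of progressive disease (PD) is the date of initial observed clinical or radiographic PD". Protocol Section 7.9.1 states: "For analysis purposes, date of PD is the date of initial observed PD", and Section 7.2.2 says the same. The SAP Section 5 PFS event is the "date of radiological evidence of disease progression (date of MRI scan) or death, regardless of cause". The SAP TTP event is the initial date of the first radiographic PD on MRI. None of these mentions a confirming scan.

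**Censoring.** SAP Section 5 states: "If a subject's disease has not progressed and the subject is alive, progression-free survival time will be censored". The censoring date is the last date the subject is known to be free of progression, which the SAP equates with the last evaluable scan. Subjects who withdraw consent are censored there too, but only if they withdraw before progression.

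**What ends observation.** Section 7.9.1 plans a confirmatory MRI at least 4 weeks after a first PD scan. The same section ends imaging at new treatment, consent withdrawal or evident clinical progression. Section 7.2.5 ends long-term follow-up at new therapy. Section 8.3.2 lists "start of any other antitumor therapy" as a reason for removal from the study.

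**The concern.** Take a subject whose week-11 scan shows growth of at least 25% and who starts another therapy at week 13. No confirmatory scan is done. Under the PD definition in SAP Section 5 this growth is not PD, so the subject has not progressed and is censored. Under the PFS and TTP event definitions in the same section, the week-11 scan is the event.

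The subjects in this position are likely to be those who progress fastest, because they are the ones who switch treatment or decline before a second scan. Censoring them removes people from the risk set because they progressed, which is informative censoring, and it biases Kaplan-Meier PFS, TTP and the 6- and 12-month rates upward. A confirmation rule is meant to screen out pseudoprogression, meaning growth that a later scan refutes. Growth that was never re-imaged has not been refuted.

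**Working it through.** The plan states no PFS or TTP assumption, so there is no document figure to reproduce. The check has two parts: comparing the wording, and illustrating the size under the confirmed-only reading.

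**1. Which reading does the text support?**

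- For confirmed-only: the TTP definition uses the term PD, which SAP Section 5 itself defines with confirmation. Taking the initial date of the first PD is compatible with backdating a confirmed PD.
- For first PD: where the SAP wants confirmation in an endpoint definition, it says so. Duration of response starts at a response that is later confirmed, and time to response runs to the confirmation date. PFS and TTP have no such words. Three places in the protocol date PD at first observation.

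Both readings are open, and no sentence chooses between them.

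**2. Size under the confirmed-only reading**

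Inputs:

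- Two scans, at about weeks 11 and 22 (Section 7.9.1 gives every 10 to 12 weeks).
- True progression-free rate S after the second scan: 30% or 20%, assumed.
- Share u of first PDs never confirmed: 10%, 20% or 30%, assumed because the documents do not give it.
- Same progression probability at each scan, p = 1 − √S. For S = 0.30, p = 0.452. For S = 0.20, p = 0.553.

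The censoring date is itself open, because a scan showing growth may be the last evaluable scan but is hard to call progression-free.

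- Censored at the PD scan, the Kaplan-Meier estimate is (1 − (1−u)p)². For S = 0.30, u = 0.2: (1 − 0.8 × 0.452)² = 0.638² = 0.407.
- Censored at the previous scan, it is ((1−p)/(1−up))². For S = 0.30, u = 0.2: (0.548/0.910)² = 0.602² = 0.363.

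| True rate | Censored at | u = 10% | u = 20% | u = 30% |
|---|---|---|---|---|
| 30% | previous scan | 33% | 36% | 40% |
| 30% | PD scan | 35% | 41% | 47% |
| 20% | previous scan | 22% | 25% | 29% |
| 20% | PD scan | 25% | 31% | 38% |

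Counting the first PD returns the true 30% or 20%.

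**3. Effect of captured deaths on PFS**

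A simulation of 200,000 subjects used exponential progression, 11-week scans and a true 26-week rate of 25.3% (a published rate cited in protocol Section 2.1, used here only as an assumption). Counting first PD gives 31.4%, above 25.3% because progression is seen only at scans. With u from 10% to 40%:

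- censoring at the PD scan gives 36.6% to 54.2%;
- censoring at the previous scan gives 34.4% to 46.2%;
- censoring at the PD scan, but with half of the later deaths captured as events (assumed mean 20 weeks to death), gives 35.9% to 49.9%.

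Captured deaths reduce the PFS bias without removing it. The TTP definition does not count death, so TTP gets no such relief.

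**The case against.** A reader might infer that the plan censors unconfirmed PD and therefore inflates PFS and TTP. The documents do not support that as the plan's single rule. No sentence says an unconfirmed PD is censored, and the SAP's event definitions, read literally, count it. That objection stands, and it is why the point is a conflict with a missing rule and not an established bias.

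Three related inferences also go too far.

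- **Clinical decline.** Table 22 lists "or substantial clinical decline" as a PD criterion in its own right, and the confirmation line speaks of an increase. The synopsis counts clinical PD, while SAP PFS and TTP count only radiological progression. That is a separate conflict, not a result of the confirmation rule.
- **Later deaths.** It is too strong to say they are lost. Section 7.2.5 keeps access to medical records for up to 12 months from treatment start, Section 12.4 allows searches of public records for survival status, and the SAP follows survival where possible after treatment withdrawal. A captured death is still a PFS event.
- **Withdrawal.** The SAP censors withdrawal only before progression, which leaves withdrawal after a first PD scan undecided.

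A second scan may also come from the safety follow-up visit, which Section 7.2.4 keeps even if another therapy has begun. That helps only in part. Imaging there is required only when the last scan was more than 6 weeks (42 days) earlier, and the visit falls at most 37 days after the last dose. If dosing stopped by the time of the PD scan, no scan is required.

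It is also fair to say that PFS and TTP are secondary and descriptive, that no formal external comparison is planned, and that the landmark in protocol Section 10.5.3 is a simple proportion. The formulas above describe the SAP's Kaplan-Meier analysis, not that proportion.

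**Conclusion.** The documents give two answers for a subject whose first PD scan is never repeated. Under the confirmed-only answer, Kaplan-Meier PFS and TTP are biased upward; under the other there is no inflation. For a true 30% and 10% to 30% of PDs unconfirmed, the bias is about 3 to 10 percentage points if censoring is at the previous scan and 5 to 17 points if it is at the PD scan. These figures rest on an assumed unconfirmed share, two scans with equal progression probability, and no captured deaths. The direction follows from censoring subjects because they progressed; the size is illustrative only.

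ORR, the Group 2 futility rule and the primary safety endpoint do not depend on the PD rule and are unaffected. The point is worth correcting before analysis because the missing scans are foreseeable and the choice would otherwise fall to whoever programs the endpoint.

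**What to change.** Add to SAP Section 5, for the PFS and TTP analyses only: a first radiographic PD is an event dated at first observation, unless a scan at least 4 weeks later and before any new antitumor therapy does not meet PD. A first PD with no later scan counts as an event at first observation.

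Report the confirmed-only analysis as a sensitivity analysis, with its censoring date stated. Align the Appendix D dating sentence in both documents for analysis purposes. The response categories and the treatment-continuation rules need not change.

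The cost is wording. The first PD scan is already collected, so no new data are needed. The downside is that a few pseudoprogressions that are never re-imaged will count as events, so reported PFS will be slightly lower.

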Appendix E. Grading and Management of Cytokine Release Syndrome (CRS)

| CRS Grade | Description of Severity ^a | Minimum Expected Intervention | Instructions for Interruption of Dosing |
|-----------|---|---|---|
| 1 | Symptoms are not life threatening and require symptomatic treatment only, eg, fever, nausea, fatigue, headache, myalgias, malaise | Administer symptomatic treatment (eg, paracetamol/acetaminophen for fever). Monitor for CRS symptoms including vital signs and pulse oximetry at least Q2 hours for 12 hours or until resolution, whichever is earlier. | N/A |
| 2 | Symptoms require and respond to moderate intervention Oxygen requirement < 40%, OR Hypotension responsive to fluids or low dose of one vasopressor, OR Grade 2 organ toxicity or grade 3 transaminitis per CTCAE criteria | Administer: Symptomatic treatment (eg, paracetamol/acetaminophen for fever) Supplemental oxygen when oxygen saturation is < 90% on room air Intravenous fluids or low dose vasopressor for hypotension when systolic blood pressure is < 85 mmHg. Persistent tachycardia (eg > 120 bpm) may also indicate the need for intervention for hypotension. Monitor for CRS symptoms including vital signs and pulse oximetry at least Q2 hours for 12 hours or until resolution to CRS grade ≤ 1, whichever is earlier. For subjects with extensive co-morbidities or poor performance status, manage per grade 3 CRS guidance below. | Immediately interrupt dosing until event resolves to CRS grade ≤ 1 but for no less than 72 hours. Permanently discontinue AMG 596 and AMG 404 if there is no improvement to CRS ≤ grade 1 within 7 days. |

Footnotes defined on the next page of the table

Approved

**Appendix E. Grading and Management of Cytokine Release Syndrome (CRS)
 (Continue)**

| CRS Grade | Description of Severity ^a | Minimum Expected Intervention | Instructions for Interruption of Dosing |
|-----------|---|--|---|
| 3 | Symptoms require and respond to aggressive Intervention Oxygen requirement $\geq 40\%$, OR Hypotension requiring high dose ^b or multiple vasopressors, OR Grade 3 organ toxicity or grade 4 transaminitis per CTCAE criteria | Admit to intensive care unit for close clinical and vital sign monitoring per institutional guidelines. Administer dexamethasone (or equivalent) IV at a dose maximum of 3 doses of 8 mg (24 mg/day). The dose should then be reduced step-wise. Investigators may also consider use of Tocilizumab as an additional therapy in this setting at a dose of 4-8 mg/kg as a single dose. | Immediately interrupt dosing until event resolves to CRS grade ≤ 1 but for no less than 72 hours. Permanently discontinue AMG 596 if there is no improvement to CRS \leq grade 2 within 5 days or CRS \leq grade 1 within 7 days. |
| 4 | Life-threatening symptoms requirement for ventilator support OR Grade 4 organ toxicity (excluding transaminitis) per CTCAE criteria | Admit to intensive care unit for close clinical and vital sign monitoring per institutional guidelines. Administer dexamethasone (or equivalent) IV at a dose maximum of 3 doses of 8 mg (24 mg/day). Further corticosteroid use should be discussed with the Amgen medical monitor. Additionally, Tocilizumab can be considered administered at a dose of 4-8 mg/kg as a single dose and may be repeated once within 24 to 48 hours based on clinical assessment. | Immediately stop the infusion and permanently discontinue AMG 596 and AMG 404 therapy. |

CRS: Cytokine release syndrome; CTCAE: Common terminology criteria for adverse events; IV: Intravenous

^a Revised grading system for cytokine release syndrome (Lee et al, 2014)

^b High dose vasopressors (all doses are required for ≥ 3 hours): Norepinephrine monotherapy $\geq 20 \mu\text{g}/\text{min}$; Dopamine monotherapy $\geq 10 \mu\text{g}/\text{kg}/\text{min}$, Phenylephrine monotherapy $\geq 200 \mu\text{g}/\text{min}$, Epinephrine monotherapy $\geq 10 \mu\text{g}/\text{min}$; If on Vasopressin, Vasopressin + Norepinephrine equivalent of $\geq 10 \mu\text{g}/\text{min}$; If on combination vasopressors (not Vasopressin), Norepinephrine equivalent of $\geq 20 \mu\text{g}/\text{min}$

Approved

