6.2.4 Dosage Adjustments, Delays, Rules for Withholding or Restarting, Permanent Discontinuation

6.2.4.1 AMG 596

Dose Delay or Dose Reduction

Any clinically relevant (as determined by the investigator) grade 4 adverse event related to IP that does not meet the DLT criteria should lead to a dose delay and/or a dose reduction. The decision if a dose delay or reduction will be performed is up to the investigator's discretion. The sponsor may be consulted.

In addition, cytokine release syndrome of \geq grade 3 ([Appendix E](#)) should lead to dosing interruption and treatment with immunosuppressive therapies should be performed (see [Section 6.3](#) for details).

In case of re-appearance of the same grade 4 adverse event, IP should be permanently discontinued.

For persistent or re-occurring clinically relevant grade 3 adverse event related to IP, a dose delay or a dose reduction should be considered.

Infusion Interruption

Significant events requiring a change in treatment will be managed by immediate infusion interruption and should be documented in source documents and in the eCRF:

- The subject experiences a DLT as defined in [Section 6.2.3](#).
- The subject experiences a clinically relevant grade 4 adverse event related to IP (see above)
- The subject meets criteria for discontinuation of IP as described in [Section 8.3](#)
- Technical problem with the infusion pump
- The investigational product is incorrectly prepared or administered (eg, overdose)

Restarting the Infusion

Treatment may resume if the interruption is \leq 21 days:

- If the interruption occurred due to other reasons than toxicity (technical or logistic reasons; eg, diagnostic measurements). The infusion can be restarted at the same dose and without additional measures or delays.
- The toxicity has resolved to \leq grade 1. The infusion can be restarted according to guidelines presented in [Table 3](#) and [Table 4](#). Non-hematological Criteria for Dose Reduction.
- The toxicity occurred during the DLT period and has resolved to grade 2. The infusion can only be restarted in an individual subject with a clear clinical benefit from treatment after consultation with the sponsor on a case-by-case basis.

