6.3.1 Cytokine Release Syndrome (CRS)

Cytokine release syndrome is clinically defined and may have various manifestations. Most cancer immunotherapies bear the risk of cytokine-associated toxicity, also known as cytokine release syndrome caused by non-antigen specific high level immune activation ([Lee et al, 2014](#) and [Appendix E](#)). Signs and symptoms of CRS may include:

- Constitutional – fever, rigors, fatigue, malaise
- Neurologic – headache, mental status changes, dysphasia, tremors, dysmetria, gait abnormalities, seizure
- Respiratory – dyspnea, tachypnea, hypoxemia
- Cardiovascular – tachycardia, hypotension
- Gastrointestinal – nausea, vomiting, transaminitis, hyperbilirubinemia
- Hematology – bleeding, hypofibrinogenemia, elevated D-dimer
- Skin – rash

Subjects may be at an increased risk for cytokine release syndrome during the first few days following the initial infusion of AMG 596 and/or AMG 404. Cytokine release syndrome may be life-threatening or fatal. Infusion reactions may be clinically indistinguishable from manifestations of cytokine release syndrome. Throughout the infusion with AMG 596 and/or AMG 404, monitor subjects for clinical signs (eg, fever, tachycardia, dyspnea, tremors) and laboratory changes (eg, transaminase increase) which may be related to cytokine release syndrome. In the event of CRS, an unscheduled blood sample should be collected to measure cytokine levels.

Grading of cytokine release syndrome should be performed according to the recommendations provided by [Lee et al, 2014](#). (see [Section 13](#) and [Appendix E](#)).

Interventions for cytokine release syndrome will be determined by its particular manifestations and magnitude in each subject. Pyrexia may be managed with paracetamol/acetaminophen. Management of hypotension should be managed by volume resuscitation and, in the event that it is not sufficient or if there is evidence of volume overload, pressor support may be added, with the type of vasopressive agent determined by the investigator depending on the totality of observed hemodynamic parameters (heart rate, cardiac output, central venous pressure).

For grade 2 CRS, the study drug should be interrupted and monitoring and management of CRS symptoms should be performed as described above and according to published recommendations by [Lee et al, 2014 \(Appendix E\)](#). The study drug should be permanently discontinued for grade 2 CRS not improving to grade ≤ 1 within 7 days ([Appendix E](#)).

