For grade 3 or greater cytokine release syndrome, the study drug should be interrupted and immunosuppressive therapies should be provided. Corticosteroids such as dexamethasone or methylprednisolone are the preferred choice for immunosuppression. Typical doses for dexamethasone are 8 mg IV q8 hours with subsequent tapering following symptom resolution. Tocilizumab has been reported to be efficacious in this setting at a dose of 4-8 mg/kg as a single dose. However, due to the reported potential aggravation of IL-6 levels in CNS in association with tocilizumab treatment decision should include careful risk-benefit evaluation. The study drug should be discontinued for grade 3 CRS not improving to grade ≤ 2 within 5 days or grade ≤ 1 within 7 days ([Appendix E](#)).

For grade 4 cytokine release syndrome, the study drug should be interrupted immediately and permanently discontinued. The subject should be transferred to an intensive care unit ([Appendix E](#)). After observation of first DLT (in DLT period 1) associated to cytokine release-associated adverse events, step dosing and/or prophylactic treatment with steroids (dexamethasone) is recommended to mitigate the cytokine release syndrome risk in further subjects.

Prophylactic dexamethasone treatment according to the following schema will be recommended to all subject after the observation of a first cytokine release syndrome of grade 2 (see [Appendix E](#)) or higher.

- Dexamethasone at a dose of 4 to 8 mg or equivalent corticosteroid will be administered orally or IV
 - 8 to 12 hours prior to the start of the infusion on day -1
 - 1 hour prior to the start of the infusion on day 1
 - Every 8 to 12 hours after start of infusion for first 24 hours of the infusion
- Corticosteroid treatment can be continued if deemed necessary by the investigator and after consultation with the sponsor but doses should be tapered as quickly as feasible. Close monitoring of blood glucose levels is recommended in such a case. Further variations may be needed that should be discussed and agreed upon in a DLRM.

Approved

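### Appendix E permanently stops only AMG 596 for grade 3 CRS that misses its recovery limits, but stops both drugs for unresolved grade 2 and any grade 4, leaving no express bar on AMG 404 in Arm 2

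*Protocol*

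**What the plan says.** The dosing column of protocol Appendix E gives one rule per CRS grade.

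- Grade 2: "Permanently discontinue AMG 596 and AMG 404 if there is no improvement to CRS" grade 1 or lower within 7 days.
- Grade 3: "Immediately interrupt dosing until event resolves to CRS grade" 1 or lower, for at least 72 hours; then "Permanently discontinue AMG 596 if there is no improvement to CRS" grade 2 or lower within 5 days, or grade 1 or lower within 7 days.
- Grade 4: "Immediately stop the infusion and permanently discontinue AMG 596 and AMG 404 therapy", whether or not the event resolves.

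Section 6.3.1 covers the same grades without naming a product. For grade 2, "The study drug should be permanently discontinued for grade 2 CRS not improving to grade" 1 or lower within 7 days. For grade 3, "The study drug should be discontinued for grade 3 CRS not improving to grade" 2 or lower in 5 days or 1 or lower in 7. For grade 4, "the study drug should be interrupted immediately and permanently discontinued".

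Section 6.2.4.1, which carries the subheading AMG 596, says that CRS of grade 3 or higher "should lead to dosing interruption and treatment with immunosuppressive therapies should be performed". Table 4 in that section stops study treatment permanently for grade 3 CRS only if there is no recovery within 21 days, but its footnote sends CRS criteria to Appendix E. Section 6.2.5 stops the investigational products for a DLT or other unmanageable toxicity. It allows a restart after a DLT that returns to grade 1 or baseline within 14 days, given clinical benefit, agreement with the Medical Monitor and a willing subject.

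**The concern.** Stopping rules are expected to widen, or at least not narrow, as severity rises. Here a grade 3 event, which Appendix E sends to intensive care, names fewer products for permanent discontinuation than an unresolved grade 2 event does. The protocol gives no reason.

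The stake is subject safety in the combination arm. Section 6.3.1 ties CRS risk to the first infusion of AMG 596, of AMG 404, or of both, and says CRS can be fatal. Section 2.5.3.2 expects adverse events from synergistic T-cell activation and reports no clinical safety information for the combination. An investigator applying the grade 3 row literally would stop AMG 596 for good and find no instruction there about AMG 404.

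**Working it through.** No formula applies to the rule itself, so the check sets the texts side by side.

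**1. Products named for permanent stop in Appendix E**

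| CRS grade | Trigger | Products named |
|---|---|---|
| 2 | not grade ≤ 1 within 7 days | AMG 596 and AMG 404 (2) |
| 3 | not grade ≤ 2 within 5 days, or not grade ≤ 1 within 7 days | AMG 596 (1) |
| 4 | immediate | AMG 596 and AMG 404 (2) |

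The grade 3 row is the only discontinuation rule in the table that omits AMG 404.

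**2. Which text governs.** Section 6.3.1 refers to Appendix E for grades 2, 3 and 4, and the Table 4 footnote does the same for CRS. The AMG 404 section, 6.2.4.2, refers to Appendix G, which has no CRS row. The omission is therefore in the operative text.

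**3. Comparable rules.** Related grade 3 neurologic events that do not resolve within 7 days stop both drugs (Table 5). Grade 3 seizure stops the investigational products (section 6.3.2). Potential drug-induced liver injury stops both products (section 6.3.4). The Amendment 5 change list shows AMG 404 being added to the grade 2 and grade 4 stop rules while the grade 3 stop sentence kept its monotherapy form. That explains a likely origin; the defect itself is in the current table.

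**4. Recovery paths of a grade 3 event** (limits counted from onset; missing either limit triggers the stop)

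| Path | Grade 3 row | 7-day limit of the grade 2 row |
|---|---|---|
| Grade ≤ 2 by day 5 and ≤ 1 by day 7 | no permanent stop | met |
| Above grade 2 at day 5, grade ≤ 1 by day 7 | stops AMG 596 only | met, so it adds nothing |
| Above grade 1 at day 7 | stops AMG 596 only | missed, so it arguably stops both |

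The second path is the clearest residual case, because no Appendix E row reaches AMG 404.

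**5. Does section 6.2.5 catch the second path?** Within the DLT period, related grade 3 CRS still present at day 5 despite treatment has lasted more than 3 days and is a DLT under section 6.2.3. Section 6.2.5 then stops both products, but recovery by day 7 meets the time limit of the 14-day restart exception. Outside the DLT period the event is a DLT only if the DLRT decides so unanimously; otherwise only a judgement of unmanageable toxicity applies.

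**6. Time limits for recovery.** Appendix E allows 7 days to grade 1 or lower. The section 6.2.5 exception allows 14 − 7 = 7 days more. Table 4 allows 21 − 7 = 14 days more.

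**7. Population.** Arm 2 maximum: 30 + 15 + 20 + 25 = 90.

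**The case against.** The strongest reply is that other text already protects the subject. Section 6.3.1 has the same 5-day and 7-day trigger and uses one term, the study drug, for all three grades; since Appendix E names both products for grades 2 and 4, the term can be read as both for grade 3 too. Appendix H uses the same term in its AMG 404 column. A grade 3 event not at grade 1 by day 7 has also failed the milder grade's limit. AMG 404 timing is tied to AMG 596 throughout, and section 5.1 describes only monotherapy with AMG 596 or the combination.

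Much of this stands, and it limits the consequence. It does not close the gap: section 6.3.1 names no product and, for grade 3 alone, omits that discontinuation is permanent; applying the grade 2 row to a grade 3 event is an inference; and section 6.2.5 is confined to DLTs and unmanageable toxicity, with an exception.

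Three stronger readings are tempting and not supported.

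- *AMG 404 may continue during active grade 3 CRS.* The same Appendix E row interrupts dosing.
- *The protocol provides for AMG 404 alone afterwards.* No such regimen is described; it is only not expressly barred.
- *Days 8 to 14 are an open window for resuming AMG 404.* That needs a restart of treatment in section 6.2.5 to mean AMG 404 alone, and the grade 2 row's 7-day limit not to apply.

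**Conclusion.** The grade 3 permanent-stop rule in Appendix E is wrong as written for Arm 2 and should be corrected. It names 1 product where the grade 2 and grade 4 rules name 2, and the surrounding sections narrow the omission without expressly removing it. The firmest example is CRS above grade 2 at day 5 and at grade 1 or lower by day 7, especially outside the DLT period.

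This rests on two assumptions: that the day limits run from onset, and that missing either grade 3 limit triggers the stop. If both had to be missed, the day 5 to day 7 example would not trigger a stop at all, and every triggering event would also miss the grade 2 row's limit; the difference in products named would remain.

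The 90 subjects are the ceiling for Arm 2, not a count of those affected, and the documents give no expected frequency. Sample size, error rates and operating characteristics do not change.

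**What to change.** - Appendix E, grade 3 row: name both drugs in the permanent-stop sentence, as the grade 2 row does, keeping the 5-day and 7-day limits.
- Section 6.3.1: replace the unspecified study drug with both products by name, and say for grade 3 that discontinuation is permanent.
- Section 6.2.5 and Table 4: state that neither the 14-day DLT restart exception nor the 21-day recovery limit applies to CRS that has met an Appendix E permanent-stop criterion.

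The cost is a few lines of protocol wording in the next amendment. Sample size, data collection and analysis are untouched.
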